#### **6.1.4. Clot Collection and Processing**

Normally, following thrombectomy, the retrieved clot may be discarded, sent to internal departments, or retained for other purposes. However, for subjects in this study, clot samples will be collected for follow-on analysis.

Sites collecting clot for analysis will place the clot collected for each pass in a container of neutral buffered formalin solution for preservation. If more than one clot fragment is retrieved during a retrieval attempt/pass with the device, these fragments will be placed together in one container. Each container will have a unique subject identifier noting the retrieval attempt/pass number on the label. This unique identifier will be entered in the eCRF by the site along with other relevant data and linked to subject ID. Samples will subsequently be shipped by the site to the Central Lab for follow on analysis (Section 6.1.5).

All materials for collecting, processing and shipping samples to the Central Labs will be provided by the Sponsor or the Sponsor's selected vendor. For additional details on sample processing refer to Clot Collection and Processing Manual provided by Cerenovus.

#### **6.1.5. Independent Central Lab for Clot Evaluation**

Clot materials collected for this study will be processed by an independent Clot analysis lab. Standardized procedures and techniques have been established by the Core Lab for the analysis of AIS clots. These techniques comprise of morphological, histological and immunohistochemistry testing, which will help in defining clot features and in clot compositional analysis for this study.

These samples will be securely stored by the independent core lab in a study specific storage cabinet at the lab.

Samples will be sent to the core lab by the hospital in a vial with a generated "vial accession number". This number will be generated by the site and will contain no patient information. The clots will be stored in containers containing this number for identification for research purposes.

The purpose of collecting and analyzing these clots is to determine the composition of different clot types to better understand the etiology of stroke and clot types successfully removed by direct aspiration.

The following parameters of the clot will be measured/analyzed:

- Histology of the retrieved clot (including the red blood cell and fibrin content) will be measured using MSB (Martius Scarlett Blue) stain and H&E (Hematoxylin and Eosin) stain
- Immunohistochemistry to determine Platelets and Von Willebrand Factor
- Geometry of clot by measuring total weight and clot area

Additionally, samples may be tested for the presence of novel biomarkers that are associated with difficult clot retrieval by mechanical thrombectomy. Any remaining clot material will be retained and may be used in further scientific testing associated with the PERFECT study.

The Clot analysis lab will not have access to the subjects' chart/clinical records.

#### **6.1.6. Neurological Evaluations**

The following neurological evaluations will be used in this study and are part of SOC:

**NIHSS Score** - The National Institutes of Health Stroke Scale, or NIH Stroke Scale (NIHSS) is a tool used by healthcare providers to objectively quantify the impairment caused by a stroke. The NIHSS is composed of 11 items, each of which scores a specific ability between a 0 and 4. For each item, a score of 0 typically indicates normal function in that specific ability, while a higher score is indicative of some level of impairment. The individual scores from each item are summed in order to calculate a subject's total NIHSS score. The maximum possible score is 42, with the minimum score being a 0.

**The modified Rankin Scale (mRS)** - The mRS is a scale commonly used to measure the degree of disability or dependence in the daily activities in subjects following stroke or other neurologic event and is conducted by a qualified evaluator. It is a scale with seven categories ranging from no symptoms to severe disability and death. Qualifications of evaluator training will be documented for this study.

### **7. Study Schedule**

#### **7.1. Pre-Screening / Screening**

Subjects presenting with AIS to enrolling medical treatment facilities will be evaluated and treated by the physician according to the institutional practice prior to enrollment in the study. All assessment and imaging performed for this study are part of SOC for stroke treatment. Informed consent is mandatory and must be obtained before any data is captured in the eCRF.

A subject can be consented to participate in this study from the point of imaging confirming a large vessel occlusion up to 45 days post-procedure. During the eligibility screening, the investigator or designee will perform an initial evaluation of potential study subjects according to the inclusion/exclusion criteria. Post-procedure, the eligibility criterion to be confirmed will be the requirement for the EMBOVAC™ aspiration catheter and ADAPT to be attempted to be used in the first 3 passes, if required, unless evolution of care is required to remove a clot in a distal vessel of <2mm in diameter, and confirmation that all assessments were in alignment with the schedule of assessments (See Table 1 Schedule of Assessments).

For subjects in whom consent is sought, the investigator, or designee, will explain the research study to the subject and answer any questions that may arise. The possible risks and possible benefits of participation will be discussed. The subject will be asked to read, review and sign the EC approved informed consent form. The informed consent process is detailed further in Section 11.3.

All subjects screened will be documented on the Screening/Enrolment log, including the reason for non-participation for subjects who do not enroll.

If for any reason the subject does not meet the eligibility criteria when assessed by the investigator for inclusion in the study, the subject will not be considered enrolled in this study or be followed per this clinical protocol.

All subjects who provide informed consent will be entered into eCRF regardless of whether or not they participate in the study.

## 7.2. Baseline

The following baseline data will be collected and entered into the eCRF by the site:

- **Demographics** will be collected from a review of the subject's medical records to include age, gender, ethnicity etc. unless prohibited by local regulations (e.g., France)
- **Relevant medical history** will be collected from a subject interview and a review of the subject's medical records to include blood pressure, height, weight, BMI, History of smoking and diabetes etc.
- **Relevant medication history** will be collected from a subject interview and a review of the subject's medical records if necessary. Specifically, a thrombolytic agent (e.g., tissue plasminogen activator, urokinase, prourokinase) delivered prior to and during the procedure will be the only medication collected.
- CT / MR Imaging
- NIHSS
- Pre-stroke mRS Modified Rankin Scale – must be performed by a qualified evaluator

## 7.3. Procedure

The clinical decision to use the EMBOVAC™ Aspiration Catheter, as well as the revascularization procedure are independent (regardless) of the research. Physicians should follow the most current EMBOVAC™ Aspiration Catheter Instructions for Use (IFU) at all times with regards to the device compatibility, preparation and the recommended retrieval procedure. The research procedures are limited to the collection of data. Data will be collected before, during, and after use of the EMBOVAC™ Aspiration Catheter.

During the procedure, the following data will be collected:

- Total number of passes: A pass is defined as use of aspiration followed by evaluation of revascularization with angiography.
- Procedural angiography – The following will be recorded by the clinical site:
  - mTICI score per each attempted pass
  - Procedure Time defined as time from arterial puncture to complete recanalization (first mTICI  $\geq$  2b)
- Thrombectomy techniques and devices utilized per pass
- Additional interventions performed (if applicable)
- Record any reportable AEs per this protocol which occur during the procedure and up to the time of the 24hour examination.
- Clot collection per pass: this study aims to collect the clot from all subjects enrolled. However, in consideration of the urgent nature of stroke treatment, if the clot cannot be collected in a study procedure, it will not be considered a protocol deviation.

Once subject eligibility has been confirmed, the subject can be enrolled in the study.

**A subject is considered enrolled in this study once the physician confirms the subject meets all eligibility criteria and the subject or their legal representative has provided informed consent.**

A subject will not meet inclusion criteria and must not be enrolled if the EMBOVACTM Aspiration Catheter is not used for the first 3 clot removal passes for the target intracranial occlusion (unless use of another device is needed to remove clot in a distal vessel  $<2$ mm in diameter).

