### 3.3. Rescue Therapy

In order to provide an evaluation of the device, rescue therapy should not be used prior to completion of the first three passes with the EMBOVAC™ Aspiration Catheter.

Rescue therapy is defined as:

- Any change in frontline device therapy to remove the target occlusion in a vessel at least 2mm in size.
- Use of intra cranial stenting during the procedure
- Use of an intra-arterial thrombolytic agent during the procedure (e.g., tissue plasminogen activator, urokinase, prourokinase)

Progression in therapy to address thrombus/occlusion that is no longer appropriate for treatment with EMBOVAC™ (e.g., use of another device to remove distal occlusion in a vessel smaller than 2mm) will be considered an appropriate evolution in the standard of care and NOT considered rescue therapy.

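### Patients switched to another device before three EMBOVAC passes are barred from enrolment, so these failures are missing from the denominator of success without rescue

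*Protocol*

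**What the plan says.** - **Enrolment bar.** Protocol 7.3: "A subject will not meet inclusion criteria and must not be enrolled if the" EMBOVAC "Aspiration Catheter is not used for the first 3 clot removal passes for the target intracranial occlusion", unless another device is needed for clot in a distal vessel under 2 mm.
- **Timing.** Protocol 7.1: "Post-procedure, the eligibility criterion to be confirmed will be the requirement for the" use of EMBOVAC with ADAPT in the first three passes. The check is made when the course of the procedure is known.
- **Rescue.** Protocol 3.3 includes "Any change in frontline device therapy to remove the target occlusion in a vessel at least 2mm in size". It also lists "Use of intra cranial stenting during the procedure" and intra-arterial lytics. It instructs that "rescue therapy should not be used prior to completion of the first three passes" with EMBOVAC.
- **Denominator.** Protocol 10.2 and SAP 5 restrict the mITT set to enrolled subjects with at least one EMBOVAC pass, and the safety set to enrolled subjects in whom the catheter was advanced. SAP 7.5.2.1 counts rescued subjects as failures and keeps them in the denominator.
- **Records.** Protocol 7.1: "All subjects who provide informed consent will be entered into eCRF regardless of whether or not they participate in the study". The screening log covers everyone screened, "including the reason for non-participation for subjects who do not enroll". Protocol 10.6 requires that log to cover all first-line aspiration cases and to account for every EMBOVAC case.
- **Planned reporting.** SAP 7.2 gives counts for the analysis sets, early terminations with reasons, and enrolment by site for consented subjects. SAP 7.11 plans sensitivity analyses for mRS only.

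**The concern.** The same event decides both the outcome and entry to the study. A patient whose operator changes device on the target occlusion (vessel at least 2 mm) after one or two EMBOVAC passes has failed the endpoint by the protocol's own definition. The SAP's rule to count rescued subjects as failures cannot reach that patient, because he or she was never enrolled.

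The study aims to characterise real-world performance, and this endpoint separates EMBOVAC's own result from that of the devices that followed it. Losing failures here inflates the rate, and the confidence interval gives no sign of it. First Pass Effect is probably affected in the same direction, since a switch on the target occlusion usually means that the first pass did not clear it. The primary endpoint allows rescue, so the effect there has unknown direction and may be nil.

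The planned tables would not reveal the loss. Consented patients who are not enrolled would appear as an unexplained gap between two counts. Patients who never consented would appear in no table.

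**Working it through.** **The plan's own figure.** With p = 0.80 and n = 95 (100 enrolled, 5% attrition; Protocol 10.4, SAP 6): 1.96 × √(0.8 × 0.2 / 95) = 8.04 points, which matches the stated 8.0. This figure describes sampling error only and says nothing about who enters the denominator.

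**Which patients are lost**

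| Course of the procedure | Rescue under 3.3? | Enrolled? | In the denominator? |
|---|---|---|---|
| Switch on target occlusion, vessel ≥2 mm, before three EMBOVAC passes | Yes | Barred by 7.3 | No |
| Same switch after three passes | Yes | Yes | Yes, as failure |
| Other device for distal vessel <2 mm | No | Yes | Yes |
| Early stenting or intra-arterial lytic | Yes | Not clearly barred | Probably, as failure |
| EMBOVAC attempted but not used in a required pass | Depends on what followed | Inclusion criterion 4 and 7.1 suggest yes, 7.3 says no | Only if enrolled with at least one EMBOVAC pass |

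A switched patient could also be enrolled as an eligibility deviation (Protocol 14).

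**Size of the overstatement.** Let r be the reported rate and s the share of otherwise eligible EMBOVAC-first cases that are switched early and not enrolled. These are all failures, so:

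all-cases rate = r × (1 − s); gap = r × s.

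Neither s nor r is in the documents. Assume r = 0.70. Coverage is the probability that the planned exact 95% interval, with X ~ Bin(95, 0.70), contains 0.70 × (1 − s).

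| s | All-cases rate | Gap (points) | Coverage |
|---|---|---|---|
| 0 | 70.0% | 0 | 0.957 |
| 2% | 68.6% | 1.4 | 0.958 |
| 5% | 66.5% | 3.5 | 0.910 |
| 10% | 63.0% | 7.0 | 0.746 |
| 20% | 56.0% | 14.0 | 0.248 |

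At s = 6% coverage is 0.868. The margin of error at this rate is 1.96 × √(0.7 × 0.3 / 95) = 9.2 points; the gap equals it at s = 9.22 / 70 = 13.2%.

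In counts: 66/95 = 69.5% (exact interval 59.2 to 78.5%). Adding 11 missing switches as failures (11/106, about 10%) gives 66/106 = 62.3% (52.3 to 71.5%).

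**Other reported rates.** Success without rescue is a subset of the primary endpoint, so the planned 80% is a ceiling.

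| s | Gap at 80% | Coverage | Gap at 60% | Coverage |
|---|---|---|---|---|
| 2% | 1.6 | 0.953 | 1.2 | 0.956 |
| 5% | 4 | 0.877 | 3 | 0.939 |
| 10% | 8 | 0.641 | 6 | 0.826 |
| 20% | 16 | 0.082 | 12 | 0.374 |

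**Primary endpoint.** If a share q of the missing cases reached final mTICI ≥2b, the all-cases rate is 0.80 × (1 − s) + s × q. With q = 0 and q = 1, s = 2, 5, 10 and 20% gives 78.4–80.4, 76–81, 72–82 and 64–84%.

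**The case against.** The strongest reply is that the three-pass criterion is deliberate and open. Protocol 3.3 gives its purpose, and it appears in the Protocol Summary, 4.1 and 7.3. The reported rate correctly describes patients treated under it. On that view, the population of all EMBOVAC-first cases is a different target, and coverage of it is a hard standard for an interval that SAP 4 says is not for inference. This stands in part: the criterion need not change, and coverage only shows scale. But the stated aim is real-world performance, and the plan nowhere tells the reader that early switches are outside the rate.

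A second reply is that early switches may be rare. Operators need at least 20 ADAPT procedures (Protocol 4.3), and 3.3 tells them to complete three passes. A low share is plausible, and at 2% the effect is negligible. That is a reason to report the share, which sites already log.

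Third, some early rescues do enter. Inclusion criterion 4 and 7.1 ask only for an attempt at use, and SAP 7.5.2.1 provides for rescue during the first pass. That provision fits stenting, a lytic, or a switched patient enrolled as a deviation. A deliberate switch after one pass is barred under either version of the criterion.

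Finally, the log must hold a reason for non-enrolment, but not vessel size or pass number, so sites would have to check charts. That cost is real.

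**Conclusion.** The concern holds. A deliberate early switch on the target occlusion in a vessel of at least 2 mm is a failure of success without rescue by definition, and 7.3 keeps it out of the denominator. The direction is certain for this endpoint, probable for First Pass Effect and unknown for the primary endpoint.

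The size rests on two quantities outside the documents. At an assumed 70% reported rate the effect is immaterial at a 2% switch share, brings coverage below 0.90 by about 6%, and matches the margin of error at about 13%. At the planned 80% ceiling the gap reaches the stated 8-point margin at 10%. No test or stopping rule depends on it. It should be fixed because the rate's real-world meaning is affected and the remedy is cheap.

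**What to change.** 1. **SAP 7.2.** Tabulate from the screening log all EMBOVAC-first cases not enrolled, by reason. Show consented patients found ineligible separately.
2. **SAP 7.11.** Add a sensitivity rate for success without rescue: reported rate × (1 − S/E).
   - E is the number of otherwise eligible EMBOVAC-first cases on the log with at least one EMBOVAC pass, to match mITT.
   - S is the number of those not enrolled because another device replaced EMBOVAC on the target occlusion, in a vessel of at least 2 mm, before three passes. Leave out the exempt distal-vessel cases and any switched patient who was enrolled. Count cases with no EMBOVAC pass separately.
   - Illustration with assumed counts: E = 200, 20 switches of which 6 were enrolled, 126 successes. The reported rate is 126/186 = 67.7%. With S = 14, 67.7% × (1 − 14/200) = 63.0% = 126/200, as it should be; S = 20 would over-correct to 61.0%.
   - Scale the exact limits by the same factor and say that S/E is treated as known. In simulation with S random (reported rate 70%, n = 95, E = 150 or 200), coverage stayed between 0.934 and 0.955.
   - State the assumptions: switched cases would have consented equally often, and consenters represent the other non-switched cases. Note that the per-site cap (Protocol 4.3) and the exclusion of missing core-lab scores (SAP 7.5) can strain the second.
   - As a check without scaling, add consented-but-switched patients as failures. This corrects only partly, because never-consented switches remain absent.
   - Give worst and best bounds for the primary endpoint.
3. **Description and wording.** Say that the reported rate applies to patients meeting the three-pass criterion. Reconcile inclusion criterion 4 (4.1 and Protocol Summary), 7.1 and 7.3. They differ on whether an attempt at use suffices, and 7.3 omits the qualifier about three passes being needed. Which version is right, and when another device may be used, is not at issue here.

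**Cost.** Items 1 and 2 and the description need SAP text and aggregate counts from an existing log, with sites checking each counted case for eligibility, vessel size and pass number. No patient-level data from non-consenters go to the sponsor, and the work can be done after enrolment closes. Only the reconciliation needs a protocol amendment. The sponsor may report a somewhat less favourable sensitivity rate. Enrolling all EMBOVAC-first cases and recording an early switch as an outcome is an option, but is not required.

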## 4. Study Population

### 4.1. Participant Inclusion Criteria

Investigators will assess potential subjects who are candidates for the study. Candidates who meet the protocol inclusion / exclusion criteria may be enrolled. The subject selection criteria are in place for protection of participants and to address factors that may compromise the outcome of the investigation or interpretation of the results.

Candidates for this study must meet ALL of the following criteria:

1. Subject  $\geq$  18 years old.
2. Subject experiencing acute ischemic stroke with angiographic confirmation of Large Vessel Occlusion (LVO) of the distal intracranial internal carotid artery, middle cerebral artery (M1 or M2) or anterior cerebral artery (A1 or A2).
3. A clinical decision has been made to use the EMBOVAC™ aspiration catheter prior to enrollment in the research.
4. EMBOVAC™ Aspiration Catheter is attempted to be used for the first 3 clot removal passes for the target intracranial occlusion (if 3 passes are needed) using A

Direct Aspiration First Pass Technique (ADAPT). Exception: it is not considered rescue therapy if use of another device is needed to remove distal occlusion in a vessel smaller than 2mm after the first pass.

5. Pre-stroke mRS  $\leq 1$
6. NIHSS  $\leq 30$
7. Informed consent has been provided by the subject or the subject's legally authorized representative.

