### **10.2. Analysis Sets**

For the analysis of study endpoints, the analysis populations defined in the following will be used:

- Modified Intent-To-Treat (mITT) Population: The mITT population will consist of enrolled subjects who have received treatment (at least one pass) with the study device. The mITT population will be used to analyze the effectiveness endpoints.

- Safety Population (SP): The SP will consist of all enrolled subjects in whom the treatment was attempted, defined by the advancement of the EMBOVAC™ Aspiration Catheter inside of the patient. The SP will be used to analyze safety endpoints.

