A subject is considered enrolled in this study once the physician confirms subject meets all eligibility criteria and the subject signs the informed consent.

The mITT analysis set will be used to analyze effectiveness endpoints.

- **Safety Analysis Set**

The safety analysis set will consist of all enrolled subjects in whom the treatment was attempted, defined by the advancement of the EMBOVAC Aspiration Catheter inside of the subject.

The safety analysis set will be used to analyze safety endpoints.

6 Sample Size Justification

There is no statistical power calculation and no hypothesis tests for this post-market study. 100 subjects are deemed sufficient to characterize the performance of EMBOVAC Aspiration Catheter.

Approximately 100 subjects will be enrolled. With an enrolled sample size of 100 and an attrition rate of no more than 5%, the precision (margin of error) for the primary endpoint is anticipated to be around 8.0% based on 2-sided 95% confidence intervals, where the primary endpoint rate is estimated to be 80%.

$$\text{Margin of error} \approx 1.96 \times SE = 1.96 \times \sqrt{\frac{p(1-p)}{n}} = 1.96 \times \sqrt{\frac{0.8 \times (1-0.8)}{95}} = 8.0\%$$

where SE denotes the standard error and p denotes the proportion of subjects who achieve the primary endpoint.

7 Analyses to be Conducted

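### Protocol 7.3 requires EMBOVAC to have been used where inclusion criterion 4 and section 7.1 require only an attempt, so membership of the safety set depends on which section a site applies

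*Protocol*

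**What the plan says.** Three places in the Protocol accept an attempt. Inclusion criterion 4 (section 4.1, repeated in the Protocol Summary) is met if the EMBOVAC "Aspiration Catheter is attempted to be used for the first 3 clot removal passes for the target intracranial occlusion", qualified by whether three passes are needed. Section 7.1 names this as a criterion to be confirmed after the procedure: the EMBOVAC "aspiration catheter and ADAPT to be attempted to be used in the first 3 passes, if required".

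Section 7.3 is stricter. It says a subject fails the inclusion criteria and must not be enrolled if the EMBOVAC "Aspiration Catheter is not used for the first 3 clot removal passes for the target intracranial occlusion". It keeps the exception for distal vessels under 2 mm, but mentions neither an attempt nor whether three passes are needed. The same section defines a pass as aspiration followed by angiographic evaluation, so advancing the catheter without aspirating is not a pass.

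The analysis sets are built on enrolment. SAP section 5 defines the safety set as "all enrolled subjects in whom the treatment was attempted, defined by the advancement of the EMBOVAC Aspiration Catheter inside of the subject", and Protocol 10.2 agrees. For effectiveness, Protocol 10.2 states: "The mITT population will consist of enrolled subjects who have received treatment (at least one pass) with the study device". Under section 7.1, if a candidate fails eligibility, "the subject will not be considered enrolled in this study or be followed per this clinical protocol".

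**The concern.** The safety set is defined more widely than the mITT set. What separates them is mainly the subject in whom the catheter was advanced but no EMBOVAC pass was completed. That is the subject on whom 7.3 disagrees with 4.1 and 7.1.

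Harm or device deficiency during navigation is something a failed attempt could cause. If such a subject is not enrolled, the case drops out of the device-related SAE rate, sICH, 24-hour NIHSS and 90-day mortality. Nothing in the documents brings it back:

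- Section 8.2.4 has adverse events assessed for enrolled subjects.
- The screening log in section 10.6 records the case and the reason for non-enrolment, but no analysis takes in its events.
- Section 7.1 enters every consented person in the eCRF, but gives ineligible ones no follow-up and no analysis set.

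Timing adds to the problem. The criterion is checked after the procedure and consent may follow up to 45 days later, so a site applies an ambiguous rule already knowing how the device behaved. Section 1.3 reports no earlier clinical investigation of this catheter, and SAP 7.9 sends interim summaries to regulators.

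**Working it through.** **Step 1. The plan's own figure.** The only design calculation is the margin of error for the primary endpoint: 1.96 × √(0.8 × 0.2 / 95) = 8.04%, which agrees with the stated 8.0%. It does not bear on this point. The documents give neither a failed-attempt share nor an expected device-related SAE rate.

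**Step 2. The sections applied to the same subjects.**

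| Course of the procedure | Criterion 4 and 7.1 | 7.3 as worded | Set affected |
|---|---|---|---|
| Catheter advanced, no EMBOVAC pass, another device makes the passes | Eligible, if the advancement counts as the attempt | Barred | Safety |
| EMBOVAC makes pass 1, an attempt at pass 2 or 3 fails, another device takes over | Eligible | Barred | Safety and mITT |
| EMBOVAC makes all needed passes but does not reperfuse | Eligible | Eligible when three EMBOVAC passes were made | None |
| Vessel cleared in one EMBOVAC pass | Eligible | Arguably barred, since the qualifier on needed passes is absent | Shows loose drafting |
| Catheter advanced, procedure ends with no pass by any device | Not settled | Not clearly barred | Safety |

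The first row concerns membership of the safety set. The second reaches the primary endpoint as well, because such a subject has one pass and would be in mITT if enrolled.

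**Step 3. Possible size for the device-related SAE rate.** Let f be the share of device attempts that made no EMBOVAC pass and are dropped, r_u the SAE rate in subjects with a pass, and r_f the rate in the dropped subjects. These are treated as simple proportions; the SAP's Kaplan-Meier estimate would also handle censoring.

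- Rate with all attempts included = (1 − f) × r_u + f × r_f
- Bias from dropping them = r_u − [(1 − f) × r_u + f × r_f] = −f × (r_f − r_u)

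All inputs are assumptions: f = 2, 5 or 10%; r_u = 1, 3 or 5%; r_f from 0 to 30%. At r_u = 3%, the bias in percentage points is:

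| r_f | f = 2% | f = 5% | f = 10% |
|---|---|---|---|
| 0% | +0.06 | +0.15 | +0.30 |
| 3% | 0 | 0 | 0 |
| 10% | −0.14 | −0.35 | −0.70 |
| 20% | −0.34 | −0.85 | −1.70 |
| 30% | −0.54 | −1.35 | −2.70 |

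One cell worked through, f = 5% and r_f = 20%: 0.95 × 3% + 0.05 × 20% = 3.85%, against 3% reported.

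Extremes of the whole grid:

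- r_u = 1%, r_f = 30%, f = 10%: full rate 0.9% + 3.0% = 3.9%, bias −2.9 points.
- r_u = 5%, r_f = 0%, f = 10%: full rate 4.5%, bias +0.5 points.

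For scale, the exact 95% interval is 0.7% to 9.0% for 3 events in 95 subjects and 1.1% to 9.9% for 4 in 100. Most of the grid is small beside that imprecision, but the interval does not reflect a selection effect.

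**The case against.** The strongest reply is that 7.3 sets no separate rule. It says who fails the inclusion criteria, so it points back to criterion 4, which accepts an attempt. Section 7.1, which specifies the post-procedure check, accepts an attempt too. Read literally, 7.3 could bar a subject cleared in one pass, which would make no sense beside the first-pass endpoints, so sites are unlikely to apply it word for word. The safety-set definition itself presupposes enrolled subjects without a pass. There is no hypothesis test, and SAP 4 offers the intervals for clinical reference only. SAP 7.2 already reports the size of each analysis set, and the screening log would show the exclusions.

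Much of this stands. A reader might infer that the plan empties the safety set of failed attempts and biases the device-related SAE rate low. The documents do not support that as a fact:

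- The set shrinks only where a site puts 7.3 above 4.1 and 7.1. Even then, a procedure that ended before any pass is not clearly barred.
- The bias is downward only if r_f exceeds r_u. That is plausible, but no document figure shows it.
- Subjects in whom EMBOVAC was used without success are not, for that reason alone, excluded by either wording.

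What the reply does not remove is the conflict. Section 7.3 is phrased as a prohibition and stands beside the definition of enrolment, so a site could reasonably follow it. The log would show that a case was left out, but not what happened to the patient.

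**Conclusion.** The point holds as a conflict over enrolment that passes into the analysis sets. Whether an advanced-but-no-pass subject counts in the safety denominators depends on the section a site applies, and the decision is taken after the procedure. This conclusion needs no assumed rate; it rests only on reading an advancement without a pass as an attempt but not as use.

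If 7.3 is followed, the safety set largely coincides with mITT, and the device-related SAE rate is understated if failed attempts carry the higher SAE rate. Size and direction cannot be settled from the documents: the assumed grid gives about −2.9 to +0.5 points, with zero where the two rates are equal. No size was worked out for sICH, 24-hour NIHSS, mortality or the primary endpoint. It should be corrected because the remedy is cheap and the cases at risk are those the wider safety set was written to hold.

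**What to change.** 1. Reconcile Protocol 7.3 with inclusion criterion 4 (section 4.1 and the Protocol Summary) and with 7.1, so that one eligibility wording applies. It should carry both elements: attempted use, and the limit to as many of the three passes as are needed. Changing only the verb in 7.3 would leave the second element in conflict. Subjects with the catheter advanced but no pass can then be enrolled and counted as Protocol 10.2 and SAP 5 define the safety set.
2. In the disposition table, report the number in the safety set but not in mITT, and the number of screening-log EMBOVAC cases not enrolled because the device was not used.
3. If the sponsor prefers to keep the 7.3 rule, state that the safety rates apply only to subjects in whom the device was used.

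The cost is one clarifying protocol sentence and two disposition rows. A few more subjects would need consent and follow-up, and the safety rates might come out slightly less favourable.
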